Study 1: Exploratory study - identifying the benefits of pMDI versus Diskus for delivering fluticasone/salmeterol combination therapy in patients with chronic obstructive pulmonary disease (COPD)

Version Date: 7 February 2014

Protocol

**Study 1: Exploratory study -
identifying the benefits of pMDI
versus Diskus for delivering
fluticasone/salmeterol combination
therapy in patients with chronic
obstructive pulmonary disease
(COPD)**

To characterise patients with COPD initiating with fluticasone/salmeterol combination therapy via pMDI and Diskus and to identify and compare the potential benefits of using either device in the delivery of fluticasone/salmeterol combination therapy

Contents

OBJECTIVES	3
BACKGROUND	3
DATASOURCE	4
STUDY DESIGN	4
STUDY OUTCOMES	7
STATISTICAL ANALYSIS.....	8
TIMELINE, DELIVERY AND COSTINGS	9
RESEARCH TEAM	9
REFERENCES.....	9

OBJECTIVES

The aims of this exploratory study are to characterise patients with chronic obstructive pulmonary diseaseⁱ (COPD) initiating with fluticasone/salmeterol combination therapy delivered via pressurised metered dose inhaler (pMDI; also known as Evohaler) or Diskus (also known as Accuhaler); and to identify and compare the potential benefits of using either device in the delivery of fluticasone/salmeterol combination therapy.

This will be carried out by:

- (1) Characterising patients with COPD on fluticasone/salmeterol combination therapy via pMDI and Diskus.
- (2) Identifying and comparing the potential benefits of using pMDI versus Diskus in the delivery of fluticasone/salmeterol combination therapy in terms of both efficacy and adverse events, in particular:
 - a. Number of COPD exacerbations
 - b. Development of pneumonia infections
 - c. Type II diabetes diagnosis
 - d. Therapeutic indexⁱⁱ
 - e. Number of severe COPD-related events, including:
 - i. Lower respiratory tract infections
 - ii. Oral thrush

These are more clearly defined under 'Dataset Variables' below.

BACKGROUND

Inhaled corticosteroid use by patients with obstructive lung disease is associated with increased risk of pneumonia [1], increased risk of developing type-II diabetes [2] and increased risk of oral thrush [3].

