STUDY DESIGN

The study will be a retrospective database analysis, consisting of a (one year) baseline period, a (one year) outcome period and an index date, defined as the date of the first prescription for Seretide[®] combination therapy at which patients with evidence of COPDⁱⁱⁱ will be split into the following groups:

- (1) Those using pMDI (also known as Evohaler)
- (2) Those using Diskus (also known as Accuhaler)

The baseline period will be one year prior to and including the index date^{iv} and it will be used for patient characterisation, such as demographics, baseline therapy, disease severity and number of COPD exacerbations. The outcome period will be one year following the index date, and the effect of device on COPD-related severe exacerbations, adverse events and therapeutic index will be investigated.

ⁱⁱⁱ COPD diagnostic code (at any time) and recorded spirometry data supporting COPD diagnosis within 5 years window of diagnosis code. Note that individuals with asthma and bronchiectasis will not be excluded.

^{iv} except for therapy prescribed at IPD (which is included in the outcome).

[figure not shown]

Figure 1: Study design

Inclusion Criteria

In order to be included in the study, patients must fit the following criteria:

- (1) COPD diagnosis (COPD diagnostic code (at any time) and COPD confirmed by FEV/FVC ratio <0.7 ever in medical history. Note that individuals with asthma and bronchiectasis will not be excluded)
- (2) Two years of continuous practice data comprising 1 year baseline data and 1 year outcome data
- (3) ≥2 prescriptions for Seretide® pMDI OR Seretide® Diskus during 1 year outcome period, inclusive of IPD (i.e. 1 Seretide® prescription at IPD plus ≥1 prescriptions for the same device during 1 year outcome period).
- (4) Age ≥35 at time of initiating with Seretide

Exclusion Criteria

- (1) Evidence of restrictive lung disease other than bronchiectasis (diagnostic code)
- (2) ≥1 prescription for inhaled corticosteroids (ICS), including as part of a fixed dose combination, during baseline period (excluding IPD)
- (3) Evidence of pneumonia during baseline period (diagnostic code)
- (4) No maintenance oral steroids in baseline

Dataset Variables

Demographics (gender, age, weight, height, BMI, smoking status, disease severity (FEV1 percent predicted, FEV1/FVC ratio, GOLD group, mMRC score)) will be calculated at (or closest to) the IPD. Disease severity will be regarded as missing if >5 years either side of IPD.

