- Development of pneumonia (recorded as absence/presence of, and confirmed via: chest X-ray within a month of a pneumonia diagnosis OR hospitalisation within a month of a pneumonia diagnosis). Note that baseline values will be zero due to study exclusion criteria.
- Development/progression of diabetes
 - Development of diabetes (recorded as absence or presence of) during outcome period for patients (for patients without diabetes at or prior to IPD)
 - Progression of ongoing type-II diabetes treatment to insulin (defined as no insulin prescription during 1 year baseline period AND any insulin prescriptions during 1 year outcome period)
 - Diabetic control (defined as change in HbA1c value prior to starting Seretide® and after IPD)
 - Diabetic medication (defined as change in anti-type-II diabetic medication dosage OR medication type)
- Number of potential severe COPD-related adverse events and date of event including
 - Oral thrush
 - Lower respiratory tract infections
 - Bronchitis
 - Dysphonia / hoarseness
 - Nasopharyngitis (common cold)
 - Sinusitis
 - Hypokalemia (low blood potassium)
 - Muscle or joint pain
- ICS dose (in outcome period only) and date of ICS prescription

Matching will be used if required.

STUDY OUTCOMES

The primary aim of the current study is to identify baseline and outcome characteristics of patients with COPD initiating with Seretide® combination therapy via pMDI and Diskus and to identify and compare the potential benefits of using each device in the delivery of Seretide®. Among other events, the effect of device on the following outcomes will be investigated:

(1) COPD related severe exacerbations

Where an exacerbation is defined as an occurrence^{vii} of:

- COPD-related: Unscheduled hospital admission / A&E attendance^{viii}; OR
- An acute course of oral steroids prescribed with evidence of a respiratory review^{ix};
OR

-
- b) Asthma/COPD review codes excl. any monitoring letter codes;
 - c) Lung function and/or asthma monitoring.

^{vii}Where ≥ 1 oral steroid course / hospitalisation / antibiotics prescription occur within 2 weeks of each other, these events will be considered to be the result of the same exacerbation (and will only be counted once).

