^{viii}**COPD-related Hospitalisations:** consist of either a definite COPD Emergency Attendance or a definite COPD Hospital Admission; OR a generic hospitalisation read code which has been recorded on the same day as a **Lower Respiratory Consultation*** (see below - excluding where the only lower respiratory code recorded on that day was for a lung function test).

^{ix}**Evidence of a Respiratory Review** - consists of the following:

- Antibiotics prescribed with evidence of a respiratory review^{ix}.

(2) COPD related adverse events

Where adverse events include the number of incidences of:

- Oral thrush
- Lower respiratory tract infections
- Bronchitis
- Dysphonia / hoarseness
- Nasopharyngitis (common cold)
- Sinusitis
- Hypokalemia (low blood potassium)
- Muscle or joint pain

(3) Therapeutic index

Therapeutic index = highest dose not causing harm (side effect) / lowest dose that causes benefit (reduced number of severe COPD-related events).

For the highest dose not causing harm: the median dose at which no (any) adverse events occur

For the lowest dose that causes benefit (reduced number of severe COPD-related events): median dose at which patients show no increase in number of exacerbations in outcome

STATISTICAL ANALYSIS

Statistically significant results will be defined as $p < 0.05$ and trends as $0.05 \leq p < 0.10$

Summary statistics will be produced for all baseline and outcome variables, as a complete dataset and by device. For variables measured on the interval or ratio scale, these will include:

Sample size (n) & percentage non-missing

Mean & Variance / Standard Deviation

Range (Minimum / Maximum)

Median & Inter-quartile Range (25th and 75th percentiles)

For categorical variables, the summary statistics will include:

Sample size (n)

Range (if applicable)

Count and Percentage by category (distribution)

Treatment arms will be compared using t-test / Mann Whitney U-test (depending on distribution) for variables measured on the interval/ratio scale and using a chi square test for categorical variables.

a) Any **Lower Respiratory Consultation*** (see below) and

b) Any additional respiratory examinations, referrals, chest x-rays, or events.

* **Lower Respiratory Consultations** - consist of the following:

a) Lower Respiratory read codes (including Asthma, COPD and LRTI read codes);

b) Asthma/COPD review codes excl. any monitoring letter codes;

c) Lung function and/or asthma monitoring.

TIMELINE, DELIVERY AND COSTINGS

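### Exacerbation counts fall under a t-test or Mann-Whitney rule with no selection criterion, which yields no rate ratio and, if Mann-Whitney is used, loses power for a question about numbers of events

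*Protocol*

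**What the plan says.** Objective (2)a of the protocol names the "Number of COPD exacerbations" first among the effects to compare, and Study Outcomes (1) repeats exacerbations as the first outcome. The footnotes to the exacerbation definition merge events within two weeks of each other: "these events will be considered to be the result of the same exacerbation (and will only be counted once". Episodes further apart therefore count separately, and the variable can be 0, 1, 2, 3 or more.

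Study Outcomes (2) is also in counts: "Where adverse events include the number of incidences of". The therapeutic index in Study Outcomes (3) describes benefit in terms of number: "lowest dose that causes benefit (reduced number of severe COPD-related events".

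The Statistical Analysis section then gives a single comparison rule: "Treatment arms will be compared using t-test / Mann Whitney U-test (depending on distribution) for variables measured on the interval/ratio scale". Significance is set at 0.05. Means, variances or SDs, medians and quartiles are to be summarised by device. The section names no count model, no rate ratio, no confidence interval for a device difference, and no criterion for what the distribution must look like before one test replaces the other.

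**The concern.** The question is how many exacerbations occur on each device. If the counts are skewed, the rule points to Mann-Whitney. That test responds to whether P(X<Y) + 0.5 P(X=Y) departs from 0.5. With many tied zeros, this is largely a comparison of the event-free shares. A device that reduces second and later exacerbations but leaves the first unchanged alters the mean number while barely moving that quantity.

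Two things are at stake. The main efficacy comparison may miss a real reduction in number, and its p-value comes without an estimate, with uncertainty, of how much one device reduces the rate relative to the other. Because the selection criterion is open, the quantity being tested also depends on how the data happen to look.

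**Working it through.** **Inputs from the protocol.** The outcome is a per-patient count. Follow-up is equal for all, because inclusion criterion (2) requires "Two years of continuous practice data comprising 1 year baseline data and 1 year outcome data". Alpha is 0.05; sidedness is not stated and two-sided is assumed.

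**Assumed inputs.** The protocol gives no sample size, exacerbation rate, dispersion or effect size, so there is no figure of its own to reproduce. Base case: negative binomial counts, control mean 0.8 per year, gamma shape 0.8, 500 or 1000 per arm, 1:1.

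**1. What the base case implies.**
- Event-free share: (0.8/(0.8+0.8))^0.8 = 0.5^0.8 = 0.574, so 0.426 have at least one event.
- Repeat events: 0.8 − 0.426 = 0.374 per patient-year.
- Variance: 0.8 + 0.8²/0.8 = 1.6.

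**2. Uniform 20% reduction (mean 0.64).** The variance becomes 0.64 + 0.64²/0.8 = 1.152. The standard error of the log rate ratio is √[(1.6/0.8² + 1.152/0.64²)/n] = √[(2.5 + 2.8125)/n].
- n = 500: SE = 0.103, z = |ln 0.8|/SE = 0.223/0.103 = 2.17, power = Φ(2.17 − 1.96) ≈ 58%.
- n = 1000: SE = 0.0729, z = 3.06, power ≈ 86%.

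Simulation agrees with this within a few points and supplies the Mann-Whitney figures:

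| Scenario | n per arm | Mann-Whitney | Rate-ratio test |
|---|---|---|---|
| Uniform 20% reduction | 500 | 50% | 61% |
| Uniform 20% reduction | 1000 | 79% | 88% |
| 30% of repeats prevented | 500 | 9% | 37% |
| 30% of repeats prevented | 1000 | 14% | 61% |

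Across separate simulation runs the loss for the uniform reduction was 7 to 11 points.

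**3. Repeats only.** Preventing 30% of repeats removes 0.30 × 0.374 = 0.112 events, which is 0.112/0.8 = 14% of the rate. The event-free share stays at 0.574 in both arms, which is why Mann-Whitney sees so little of it.

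**4. Sensitivity to the assumptions.** With mean 1.0, 500 per arm and a rate ratio of 0.8, Mann-Whitney against rate-test power is 72% v 80%, 57% v 68% and 39% v 51% for negative binomial dispersion k = 0.5, 1 and 2 (k is the reciprocal of the shape). With a 50% event-free share in both arms and means of 1.15 v 0.88 (rate ratio 0.77), power at 500 per arm is 20% to 31% v 89% to 92%, depending on where the repeats fall.

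**5. Behaviour when the mean rates are equal.**
- Identical distributions: Mann-Whitney rejects about 5% to 6%, as it should.
- Equal means of 0.8 but shape 1 v 0.7: it rejects 12% at 500 and 19% at 1000 per arm. With shape 1 v 0.5 it rejects about 35% and 61%. A comparison of means stays at 5% to 6%.

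**The case against.** **A t-test is one of the two named options.** It compares means, and in these settings a Welch t-test performs almost as well as the rate-ratio test. This stands. A reader might infer that the protocol commits exacerbations to Mann-Whitney; it does not. The text leaves the choice to the distribution without a criterion, and Mann-Whitney is only the natural outcome for skewed counts.

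**Rejection at equal rates is not a fault of the test's level.** A reader might infer that Mann-Whitney has an inflated false-positive rate here, even after perfect matching. That is not supported. Under perfect matching and no device effect the two count distributions coincide, and the test keeps its nominal level. Rejection at equal means needs arms that differ in shape. That is plausible in unrandomised groups, but nothing in the protocol shows it, and groups that differ in shape would often differ in mean as well. The protocol also allows matching if required.

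**An estimate is available.** It would be wrong to say that the plan yields no estimate of the number of exacerbations. Means and SDs by device are required, and with one outcome year per patient the mean is the annual rate. What is missing is a named between-device estimate with an interval.

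**The study is exploratory, and an SAP may name a count model.** Both are fair. However, the protocol does not leave the test open: it states a rule that covers these variables and attaches a significance threshold to it.

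**Conclusion.** The point holds as a cheap improvement. The stated rule is a poor fit to a question about the number of exacerbations: it has no selection criterion, its natural choice tests rank ordering, and it names no rate ratio or confidence interval. Under the base-case assumptions the cost is about 10 percentage points of power for a uniform 20% reduction. It is much larger, 9% to 14% against 37% to 61%, if a device mainly prevents repeat exacerbations. Nothing in the protocol suggests that this second pattern is the expected one, so it marks what could be lost and is not a forecast.

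All sizes rest on assumed rate, dispersion, sample size and effect pattern. The direction does not depend on the particular values tried. The point does not make Mann-Whitney invalid, and it is separate from whether the device groups are comparable: an unadjusted rate ratio would also mislead if they are not.

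**What to change.** For the exacerbation count, its separately analysed components, and any adverse-event count frequent enough to fit, specify in advance a log-link count model: negative binomial, or Poisson with robust standard errors. Report the device rate ratio with its 95% CI. No exposure offset is needed, since every included patient contributes one outcome year. If matching is used, take clustered or conditional standard errors. Keep Mann-Whitney as a descriptive supplement or for continuous variables, and present sparse adverse events as the proportion of patients affected.

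The cost is a change of analysis wording and a standard regression on data already extracted. The downside is one modelling assumption, largely covered by robust standard errors.

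### Device effects in a non-randomised comparison rest on unadjusted two-sample tests, with matching left optional and without a rule

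*Protocol*

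**What the plan says.** The Study Design section states: "The study will be a retrospective database analysis, consisting of a (one year) baseline period, a (one year) outcome period and an index date". Patients are grouped by the device first prescribed; nothing is randomised. The same section says that "the effect of device on COPD-related severe exacerbations, adverse events and therapeutic index will be investigated", and the Study Outcomes section gives part of the primary aim as "to identify and compare the potential benefits of using each device in the delivery of Seretide". The Objectives section says the same in its second aim: "Identifying and comparing the potential benefits of using pMDI versus Diskus in the delivery of fluticasone/salmeterol combination therapy".

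The Statistical Analysis section asks for summary statistics on every baseline and outcome variable, overall and by device. It then names the between-arm analysis: "Treatment arms will be compared using t-test / Mann Whitney U-test (depending on distribution) for variables measured on the interval/ratio scale". Categorical data get a chi-square test. Significance is set at p<0.05, and p from 0.05 to below 0.10 is called a trend. No other comparison of the arms is named.

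Confounding is addressed in one sentence at the end of Dataset Variables: "Matching will be used if required". Age, smoking, BMI, FEV1 % predicted, GOLD group, mMRC, co-morbidities, prior therapy and baseline exacerbations are all to be collected. The Study Design section describes the baseline year as serving to characterise patients; adjustment of the outcome comparison is not mentioned.

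**The concern.** When the prescriber chooses the device, the arms may differ in severity, asthma history or prior exacerbations before the first inhalation. A crude two-sample test cannot separate such a difference from an effect of device. Because the protocol intends to read between-arm differences as device effects and applies a significance rule to them, a difference in case mix could be reported as a benefit or harm of one inhaler. Patients with asthma or bronchiectasis are kept in, so there is room for case mix to differ.

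The optional matching does not settle this. Without a rule for when it is required, the decision can be taken after the outcome data are seen. If matching were done, the independent-samples tests named in the protocol would ignore it.

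**Working it through.** The protocol states no sample size, event rate, arm ratio or imbalance, so there is no figure of its own to reproduce. The calculations below show mechanism and range only. Every input is assumed except alpha = 0.05, which is the protocol's; two-sided testing is assumed. The true device effect is zero throughout.

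**1. Exacerbation counts, t-test**

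Assume n = 500 per arm, one arm with mean m1 = 0.9 events a year, the other with m2 = 0.9c because of case mix alone, and variance m + m² (negative binomial, dispersion 1).

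- SE = √[(v1 + v2)/n], z = (m2 − m1)/SE, rejection ≈ Φ(z − 1.96) + Φ(−z − 1.96).
- v1 = 0.9 + 0.81 = 1.71.
- c = 1.1: v2 = 0.99 + 0.9801 = 1.9701; SE = √(3.6801/500) = 0.0858; z = 0.09/0.0858 = 1.05; rejection 18%.
- c = 1.2: v2 = 1.08 + 1.1664 = 2.2464; SE = √(3.9564/500) = 0.0890; z = 0.18/0.0890 = 2.02; rejection 53%.
- c = 1.3: v2 = 1.17 + 1.3689 = 2.5389; SE = √(4.2489/500) = 0.0922; z = 0.27/0.0922 = 2.93; rejection 83%.

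Three simulation runs under the same assumptions (300 to 400 replicates each) agree:

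| Excess rate in one arm | t-test | Mann-Whitney |
|---|---|---|
| 10% | 16–19% | 15–17% |
| 20% | 51–55% | 42–45% |
| 30% | 82–85% | 71–75% |

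With no imbalance, both tests rejected in 4.5% of simulated studies, so their size is sound when the arms are alike.

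**2. Effect of sample size**

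With c = 1.1 held fixed and n = 2000 per arm, SE = √(3.6801/2000) = 0.0429, z = 0.09/0.0429 = 2.10, and rejection is 55%, against 18% at 500.

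A binary outcome behaves the same way. Assume risk 30% without and 60% with a prognostic factor whose prevalence is 40% in one arm and 30% in the other.

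- p1 = 0.4 × 0.6 + 0.6 × 0.3 = 0.42; p2 = 0.3 × 0.6 + 0.7 × 0.3 = 0.39; spurious odds ratio (0.42/0.58)/(0.39/0.61) = 1.13.
- At 1000 per arm the pooled SE is √(0.405 × 0.595 × 2/1000) = 0.02195, so the critical difference is 1.96 × 0.02195 = 0.0430. The unpooled SE is 0.02194. Rejection ≈ 1 − Φ[(0.0430 − 0.03)/0.02194] = 28%.
- At 500 and 2000 per arm the same formula gives 16% and 49%.

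**3. What adjustment buys**

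- Where the imbalance lies in one measured factor and that factor is in the model (simulated counts, mean 0.6 or 1.2 by factor, 1000 per arm, prevalence 50% against 30%), rejection falls from 53% (t-test), 44% (Mann-Whitney) and 33% (chi-square, any against none) to 5%.
- Where the imbalance lies in the underlying rate and only the prior-year count is in the model (setting of step 1), the spurious rate ratio at c = 1.2 falls from 1.20 to 1.10. Rejection falls to 7–10%, 18–27% and 35–38% for the three imbalances, depending on how dispersion is handled. The bias is reduced, not removed.
- With balanced arms, adjusting for the prior-year count lowers the SE of the log rate ratio from 0.092 to between 0.082 and 0.086, a gain of 7% to 11%.

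**4. Timing of the covariates**

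The Dataset Variables section accepts disease severity recorded up to five years on either side of the index date and takes co-morbidities whatever their timing. Entered as defined, these covariates could be post-index values already affected by treatment.

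**The case against.** The study is titled exploratory, speaks of potential benefits, and lists characterisation first, for which two-sample tests serve well. Matching is not ruled out, and an analysis plan that is not at hand may add adjustment. Matching variables, calipers, balance measures and model details are commonly left to such a plan, and their absence here is no finding. There is also some control by restriction: no inhaled steroid and no pneumonia in the baseline year, age 35 or over, and incident diabetes counted only in patients without diabetes at or before the index date.

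Much of this stands and limits the point. It does not remove it, because the protocol itself fixes crude tests as the named comparison for a stated effect of device. The exploratory label excuses limited power or uncontrolled multiplicity, not a biased contrast. Restriction does not balance severity within the eligible group.

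A reader might go further in three ways that the document does not support:

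- That confounding is shown to be present, for example that severity, age or inhaler technique drives device choice. The protocol says nothing on what drives it; confounding is possible by design, with unknown size and direction.
- That baseline data play no part in any outcome. The therapeutic index depends on patients with no increase in exacerbations, which appears to need the baseline count, and HbA1c is analysed as a change.
- That the tests are invalid for counts. The protocol chooses between t-test and Mann-Whitney by distribution, and both hold their size when arms are balanced. That exacerbation counts are overdispersed is an assumption. The remaining drawback is that the named tests give no rate ratio or interval.

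**Conclusion.** The point holds. The protocol pairs an effect-of-device aim in a non-randomised cohort with unadjusted tests at p<0.05 and an optional matching step that has no rule. If the arms differ in prognosis, following the plan as written can produce significant device differences with no device effect behind them: about 16% to 85% of null studies by t-test for a 10% to 30% difference in underlying rate, under the inputs assumed in step 1. A larger database makes this worse if the imbalance stays the same. The figures are not estimates of the bias in this study, which cannot be derived from the protocol.

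**What to change.** - Keep the t-test, Mann-Whitney and chi-square tests for baseline and descriptive summaries.
- For outcome comparisons, make adjustment mandatory and prespecified: a count model such as negative binomial for exacerbations and adverse events, and logistic regression for pneumonia and incident diabetes. Adjust for baseline-year exacerbation count, age, sex, smoking, BMI, FEV1 % predicted, mMRC/GOLD, asthma and prior respiratory therapy. Report adjusted ratios with 95% confidence intervals.
- Restrict covariates to values recorded on or before the index date.
- If matching is used, fix its rule before outcomes are seen and use an analysis that respects the matching. Regression alone would also answer the concern; propensity matching or a particular balance threshold is a matter of preference.

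The cost is protocol wording and routine analyst time; the variables are already to be collected. The drawback is missing covariates, which need a stated approach, more so once post-index values are excluded. Unmeasured confounding remains and should be acknowledged when results are reported.

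### The only formal between-arm comparison the protocol fixes, at baseline as well as for outcomes, is a significance test, which is a poor guide to baseline balance in a non-randomised device comparison

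*Protocol*

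**What the plan says.** The Study Design section of the protocol describes a non-randomised study: "The study will be a retrospective database analysis". Of the baseline year it says "it will be used for patient characterisation, such as demographics, baseline therapy, disease severity and number of COPD exacerbations".

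The Statistical Analysis section sets significance at p<0.05 and calls p from 0.05 to below 0.10 a trend. It then says "Summary statistics will be produced for all baseline and outcome variables, as a complete dataset and by device", and lists the statistics: counts, means with variance or SD, ranges, medians with quartiles, and percentages by category. The comparison rule follows: "Treatment arms will be compared using t-test / Mann Whitney U-test (depending on distribution) for variables measured on the interval/ratio scale". Categorical data are to be compared by chi-square. Nothing limits these tests to outcomes.

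The only control of confounding named is the last line of Dataset Variables: "Matching will be used if required". No criterion is attached to it.

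**The concern.** The Objectives section has two parts: to characterise the pMDI and Diskus initiators, and to compare the devices on efficacy and adverse events. Both need a sound view of how far the two groups differ at the start. Confounding bias depends on how large an imbalance is and how strongly the covariate predicts the outcome. It does not depend on how many patients were available to detect the imbalance. A p-value mixes size with number, so it can pass a material imbalance in small arms and flag a trivial one in large arms. If it were also used after matching, it could look better simply because patients had been discarded. At stake is whether a device difference in exacerbations or adverse events can be separated from differences in the patients prescribed each device.

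**Working it through.** **Inputs.** From the protocol: significance at p<0.05, trend at 0.05 to <0.10, t-test or Mann-Whitney for interval and ratio variables, chi-square for categorical variables. It gives no sample size, allocation ratio, sidedness or balance threshold, so there is no stated figure to reproduce. Assumed here: two-sided tests, the normal approximation to the two-sample t-test, a standardised difference d (difference divided by SD) of 0.20 as material and 0.05 as immaterial, and the arm sizes shown.

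**Formula.** With se = √(1/n₁ + 1/n₂), the chance of p<0.05 is Φ(d/se − 1.96) + Φ(−d/se − 1.96). For the trend threshold, 1.645 replaces 1.96.

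**Small arms, d = 0.20**

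| Per arm | d/se | Chance of p<0.05 | Not significant | Neither significant nor trend |
|---|---|---|---|---|
| 100 | 1.414 | 0.293 | 71% | 59% |
| 150 | 1.732 | 0.410 | 59% | 46% |
| 200 | 2.000 | 0.516 | 48% | 36% |

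Reaching 80% power for this difference takes 393 per arm.

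**Large arms, d = 0.05.** With 5000 per arm, se = √(2/5000) = 0.02 and d/se = 2.5, so the chance of p<0.05 is 0.705. With 10,000 per arm it is 0.942; with 100 per arm it is 0.064.

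**Observed rather than population difference.** The imbalance in the analysed cohort is what biases the result, so fix the observed d at 0.20 and use p = 2(1 − Φ(d/se)). This gives p = 0.157 with 100 per arm, 0.083 with 150 and 0.046 with 200. The same imbalance is labelled non-significant, a trend, or significant according to n alone.

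**Fewer patients, imbalance unchanged.** With the observed d held at 0.10, p is 0.046 for 500 v 2000, 0.114 for 500 v 500 and 0.221 for 300 v 300. With a population d of 0.20, going from 200 v 600 (d/se = 2.449) to 200 v 200 (d/se = 2.000) lowers the chance of p<0.05 from 0.688 to 0.516.

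**The alternative measure.** For a binary covariate, d = (p₂ − p₁)/√{[p₁(1 − p₁) + p₂(1 − p₂)]/2}. For 30% v 40% this is 0.10/√0.225 = 0.21, and for 30% v 32% it is 0.02/√0.2138 = 0.04. Arm size does not enter the formula.

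**Its limit.** The estimate still has sampling error. With no population difference, the chance that the observed d exceeds 0.10 in either direction is 2(1 − Φ(0.10/se)): 48% with 100 per arm (0.10/se = 0.707) and 32% with 200 (0.10/se = 1).

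**The case against.** The strongest reply is that the protocol already plans means, SDs and percentages by device, so the size of every imbalance will be visible and p-values are not the only evidence. That stands. It softens the point without removing it, because those summaries are given no role in deciding on matching, while the tests come with labels of significance and trend.

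A reader might infer three stronger things, and the text supports none of them:

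- *That p-values trigger matching, or certify the matched set.* The comparison rule is general, also serves outcomes, and is not linked to matching. Repeating the tests after matching is nowhere planned. The fall in significance shown above is therefore a risk, and the example assumes that matching achieved nothing. Real matching may well improve balance.
- *That matching will be decided with outcome results in view.* Baseline and outcome summaries appear in one sentence, but no order of work is stated. The text merely leaves this open.
- *That the absence of a balance measure or matching algorithm is itself the fault.* Such details may sit in a statistical analysis plan that is not at hand. The criticism is of the test rule that the protocol does fix.

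It is also fair to say that the trend band catches some of what p<0.05 misses, and that a rigid 0.10 cut-off would flag many balanced covariates in small arms. The figures and the fix allow for both. The exploratory label is a weaker defence, since the second objective compares the devices on efficacy and harm.

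**Conclusion.** The concern holds in limited form. The one formal between-arm comparison fixed in the protocol is a significance test. Read in sequence it applies to baseline variables, and it is ill suited to judging balance in a non-randomised comparison. It can mislead in either direction, depending on a sample size the protocol does not state: a 0.2 SD difference often escapes at 100 to 200 per arm, and a 0.05 SD difference is usually flagged at 5000 per arm. These percentages rest on the assumed arm sizes, two-sided tests, the normal approximation and the choice of 0.2 and 0.05 SD as material and immaterial. The dependence on n does not rest on those choices. This is a poorly chosen method that is cheap to improve. It is not a contradiction in the protocol, and it does not show that the device comparison will be biased.

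**What to change.** In the Statistical Analysis section, limit hypothesis tests to outcome variables. For baseline variables, report standardised differences between devices, before and after any matching. Those for means and proportions come directly from the summaries already planned.

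In Dataset Variables, tie the matching clause to these differences and to each covariate's prognostic relevance. A value of 0.10 can serve as a conventional guide, but not as an automatic rule, because small arms exceed it by chance as shown above. State that the decision on matching, and the matched set if there is one, are settled from baseline data before any outcome is tabulated by device.

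The cost is a few sentences and one extra table column, with no new data. The downside is that some covariates in small arms will be flagged by chance and will need a judgement.
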